3.1.3 Hypotheses

Null Hypothesis. Multi-level radiofrequency ablation of the upper airway in adults (age ≥ 22 years) with obstructive sleep apnea (AHI 10-30; Lowest O₂ sat $\geq 80\%$) results in no improvement as defined by the composite endpoint, Section 3.1.

$$\begin{aligned} H_0: \text{TT RAMOSA} &\leq \text{PG} \\ H_A: \text{TT RAMOSA} &> \text{PG}, \end{aligned}$$

where TT_{RAMOSA} is the proportion of AHI and ODI responders to the multi-level radiofrequency treatment. For this objective, the PG is established at 50%.

3.2 Sample Size Rationale

The sample size proposed for this study is 48 patients. This sample size is comparable to that used in performance and safety studies using radiofrequency ablation for the treatment of upper airways (soft palate and base of tongue, Table 1). In fact, considerable clinical data on the efficacy and safety RFA in OSAS is available from prior studies on this topic.

Recommended sample size is n=48. Sample size is calculated for o the proportion of participants who meet the successes criteria as defined by the performance goal (PG) (Section 3.1).

The following sample size considerations are based on the assumptions that PG=50% with 5% significance level and 80% power.

The sample size of n=43 +10% dropouts, i.e. n=48, is calculated by using the normal approximation for the z-score for testing inference about a single proportion p;

$$H_0: P_0 < 50\%$$

$$H_1: P_1 \geq 50\%$$

$$\text{and } P_1 - P_0 \geq 20\%$$

Below is the output of PASS12 NCSS program for sample size calculation:

Analysis of One Proportion Tests								
Numeric Results for testing $H_0: P = P_0$ versus $H_1: P > P_0$								
Test Statistic: Z Test using S (P0)								
Power	Proportion	Given H0 (P0)	Given H1 (P1)	Difference (P1 - P0)	Target Alpha	Actual Alpha	Beta	Reject H0 If Z \geq This
$\alpha=0.025$								
0.8029	187	0.5000	0.6000	0.1000	0.0250	0.0285	0.1971	1.9600
0.8112	82	0.5000	0.6500	0.1500	0.0250	0.0299	0.1888	1.9600
0.8081	43	0.5000	0.7000	0.2000	0.0250	0.0330	0.1919	1.9600
0.81	26	0.5000	0.7500	0.2500	0.0250	0.0378	0.1805	1.9600

Note that the one the actual exact Alpha of 0.033 will meet the two sided 5% significance.

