3 HYPOTHESES AND DATA ANALYSIS

3.1 Primary Efficacy Endpoints

The primary effectiveness of the study is to demonstrate a clinically significant reduction of OSAS from Baseline PSG sleep study to the 6-month follow-up PSG in adults (≥ 22 years) with obstructive sleep apnea (AHI 10-30) and BMI ≤ 32 .

Effectiveness of the CelonProSleep *plus* will be assessed by demonstrating adequate reduction in AHI and ODI as defined below:

A responder to the CelonProSleep *plus* RFA treatment is defined as a patient with an AHI reduction $\geq 50\%$ **and** a reduction of their ODI $\geq 25\%$ at the 6-month follow-up PSG, and their AHI at the 6-month follow-up is < 20 .

The aim of the study is to show that at least 50% of participants met the primary endpoint above. This will be tested with one sided 97.5% confidence interval with $\pm 20\%$ margin of error^{73, 74}.

In order to record and analyze data for determining the primary endpoints, patients will undergo a PSG sleep study to establish a mean baseline AHI and ODI. Patients will then be treated with a series of three treatments of upper airway radiofrequency ablation with the bipolar electrosurgical electrode CelonProSleep *plus* (Olympus Winter & Ibe, Germany) over 18 weeks. The patient will undergo a second PSG sleep study at the final follow-up examination 6-months later. Mean changes in AHI will be compared for each individual and among all patients. Surgical success is defined if at least 50% of participants experience at least 50% reduction in AHI and 25% reduction in ODI (Performance Goal, PG=50%).

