3.1.1 Experimental Design

This is a single-arm assessment of AHI responder rate for treatment of obstructive sleep apnea compared to a performance goal (PG). Patients with 6-month post-treatment AHI measurements will be counted as a responder if they meet the performance goal. A subject will be counted as a non-responder (regardless of AHI measurement at 6 months) under the following circumstances:

- a. Death (any cause) between treatment and the 6-month follow-up
- b. Unsuccessful radiofrequency treatment attempt
- c. Need for an alternative OSA treatment before the 6-month follow-up
- d. Subjects who abandon the study
- e. Subjects who exit the study after the last treatment, but before the 6-month follow-up

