8.1 Primary Efficacy Endpoint

The primary endpoint of AHI and ODI obtained at the 6-month follow-up will be compared to the Baseline measurement. The subject is a responder if the reduction in AHI is $\geq 50\%$, and ODI reduction is $\geq 25\%$. The proportion of subjects meeting the responder criteria among all included subjects will be evaluated using a one-sided 95% confidence interval. In addition one sample test of the proportion of patients meeting the PG at 6month is significantly different than 50%. The study is designed to demonstrate success rate of 20% beyond the PG of 50%. Proportion with 95% CI will be given using normal approximation to the Binomial. P-Value will be derived based on the exact binomial distribution of the null hypothesis, that is assuming $p=0.5$.

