8.3 Statistical Power Considerations

According to the sample size calculation (section 3.2) the actual expected power is 80.8%.

Seite 36 von 54

Protocol 990211 RAMOSA

RFA for multi-level OSA

Protocol version 6.0 from 26th September 2014

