8.5 Handling of Missing Data, Subject Withdrawals, and Treatment Failures

Subjects that are lost-to-follow-up will be categorized as treatment failures from the time point of dropout forward. Sensitivity analyses will also be conducted excluding lost-to-follow-up subjects to see what impact, if any, they might have on the overall results of clinical activity. Time-to-event analyses will consider these subjects as censored at the lost-to-follow-up time point. All data will be recorded on a CRF forms and will be subjected to regular monitoring.

Every effort will be made to follow subjects for study observation and encourage compliance with study measurements to minimize the amount of missing data.

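### The 80.8% power holds only if dropouts are left out of the primary analysis; if they are scored as non-responders, as 3.1.1 and 8.5 say, it is about 47%, and the plan does not say which rule governs.

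*Combined protocol and SAP*

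**What the plan says.** **Sizing.** Section 3.2 rests on "the assumptions that PG=50% with 5% significance level and 80% power", with an alternative 20 points above the goal, so 70%. The software output is headed "Test Statistic: Z Test using S (P0") and rejects at Z of 1.96 or more. Its row for 43 subjects gives power 0.8081 and actual alpha 0.0330. The text then reads: "The sample size of n=43 +10% dropouts, i.e. n=48, is calculated by using the normal approximation". Section 2.2 agrees: 43 subjects must supply data and 10% is allowed for dropout. Section 8.3 carries the result forward: "the actual expected power is 80.8" per cent.

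**Dropouts as failures.** Section 3.1.1 lists circumstances that make a subject a non-responder. Item d covers those who abandon the study, and item e reads "Subjects who exit the study after the last treatment, but before the 6-month follow-up". Section 8.5 says "Subjects that are lost-to-follow-up will be categorized as treatment failures from the time point of dropout forward" and leaves them out only in a sensitivity analysis.

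**Dropouts excluded.** Section 3.1.2 confines the primary efficacy analysis to subjects with all three treatments and the 6-month assessment. The Full Analysis Set in 8.4 requires all eight visits.

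**Level of the test.** Section 3.1 says "This will be tested with one sided 97.5% confidence interval". Section 8.1 says the responder proportion "will be evaluated using a one-sided 95% confidence interval", with a p-value from the exact binomial distribution.

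**The concern.** Enrolling 10% more subjects restores power when dropouts leave the denominator, because the extra subjects replace lost observations. It does not restore power when dropouts stay in the denominator with a response of zero, because each one then lowers the observed rate. Section 3.2 uses the first logic; 3.1.1 and 8.5 prescribe the second.

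This is a single-arm trial judged against a fixed 50% goal, so a few points in the overall response rate matter a great deal. If non-responder scoring is the intended primary rule, the sponsor and the regulator would be reading a power that belongs to a different analysis. The real chance of success would be close to a coin toss.

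**Working it through.** **Inputs.** P0 = 0.50, P1 = 0.70, n = 43, 10% dropout, 48 enrolled (3.2); Z >= 1.96 with variance at P0 (3.2); one-sided 97.5% interval (3.1); one-sided 95% interval and exact binomial p-value (8.1). Assumption: 70% is the rate among completers, which the inflation step implies but no section states.

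**1. The plan's own figure.** The z rule rejects when responders r >= n/2 + 1.96 x sqrt(n)/2.
- n = 43: 21.5 + 6.43 = 27.93, so r >= 28.
- P(X >= 28 | 43, 0.50) = 0.0330 and P(X >= 28 | 43, 0.70) = 0.8081. Both match the output.
- Inflation: 43/0.9 = 47.8, or 43 x 1.1 = 47.3. Both round up to 48.

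So 80.8% is right for 43 completers under the z rule.

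**2. Dropouts scored as non-responders.** Expected rate in the 48: 0.90 x 0.70 = 0.63.
- Z >= 1.96: 24 + 6.79 = 30.79, so r >= 31, with exact alpha 0.0297.
- P(X >= 31 | 48, 0.63) = 0.4743.
- With exactly 5 lost (48 - 43), the 43 completers must supply all 31 responders: P(X >= 31 | 43, 0.70) = 0.4559.

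**3. The same check across the plan's tests and levels.** The middle column is the same test on 43 completers without any dropout penalty.

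| Test | 43 completers, 70% | 48 enrolled, 63% |
|---|---|---|
| Z, one-sided 0.025 | >=28: 80.8% | >=31: 47.4% |
| Exact, one-sided 0.05 | >=28: 80.8% | >=31: 47.4% |
| Exact, one-sided 0.025 | >=29: 70.8% | >=32: 35.8% |
| Z, one-sided 0.05 | >=27: 88.3% | >=30: 59.2% |

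Against the stated 80.8% the shortfall is 33.4 points in the first two rows, 45.0 in the third and 21.6 in the fourth. In the third row, 80.8 - 70.8 = 10.0 points come from the change of test, and 70.8 - 35.8 = 35.0 from the dropout scoring.

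**4. If 70% is the overall rate, dropouts already counted as failures.** P(X >= 31 | 48, 0.70) = 0.8359. The completer rate this needs is 0.70/0.90 = 0.778.

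**5. Sensitivity to the dropout rate.** Under the z rule with 70% among completers, 5% dropout gives a rate of 0.665 and power of 67.3%. The loss does not depend on the rate being exactly 10%.

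**The case against.** The strongest reply is that 3.1.2 is the section that defines the subjects in the primary efficacy analysis, and it admits completers only. The Full Analysis Set in 8.4 and the wording of 2.2 point the same way. On that reading 43 inflated to 48 is coherent and 80.8% is correct. This stands. A reader might infer that the power is simply 47% and not 80.8%, or that the flaw survives whichever analysis set is chosen. The documents support neither: if 3.1.2 and 8.4 govern, the power figure needs no correction under the z rule, and it is the non-responder wording in 3.1.1 and 8.5 that has to go.

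A second reply is that 70% is never labelled a completer rate. Section 3.2 speaks of the proportion of participants meeting the criteria, and 8.1 of a success rate 20 points beyond the goal. If 70% is the overall rate, power at 48 is 83.6% and nothing is overstated. The inflation step favours the completer reading but does not prove it.

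A third reply concerns size. It would be too strong to say that the shortfall always exceeds 30 points: against the stated 80.8% it is about 22 points for a z-test at one-sided 0.05. Nor should 35.8% be blamed wholly on dropout scoring, since that test has only 70.8% on 43 completers.

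On the other side, 3.1.1 items d and e have no effect unless those subjects are in the denominator, 8.5 makes exclusion only a sensitivity analysis, and 8.2 calls for an intention-to-treat analysis of all enrolled subjects. Non-responder scoring is therefore a live reading of the primary rule.

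**Conclusion.** The point holds in conditional form. The calculation in 3.2 is done correctly. The defect is that it belongs to a completer analysis, while two other sections prescribe an analysis for which it is wrong.

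- If 3.1.2 and 8.4 govern, 80.8% stands under the z rule.
- If 3.1.1 and 8.5 govern and 70% is the completer rate, power is 47.4% under the sizing rule (45.6% with exactly 5 lost). It lies between 35.8% and 59.2% across the plan's conflicting alpha levels and tests, and none of these comes near 80%.
- If 3.1.1 and 8.5 govern and 70% is the overall rate, power is 83.6% under the sizing rule, at the price of an unstated completer rate of about 78%.

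The figures assume 48 enrolled and independent responses. All but the exactly-5-lost figure also assume that each subject has the same 10% chance of dropping out. The stated power cannot be relied on until the plan says which case applies, so this should be settled before the figure is used.

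**What to change.** 1. Name one primary population and one dropout rule. Amend either 3.1.2 and 8.4, or 3.1.1 and 8.5, so that all four agree. Changing only the power figure would leave 3.1.2 and 8.4 in force and add a new contradiction.
2. If dropouts are to count as failures, choose one of two statements for 3.2 and 8.3: (a) a design rate of 63% and power of about 47% under the z rule; or (b) 70% defined as the overall rate with dropouts as failures, with power of 83.6% at n = 48 and the roughly 78% completer rate it requires written out.
3. In either case, label 80.8% as the power of a completer analysis only.
4. State the test and one-sided level to which the quoted power refers, since 3.1 and 8.1 differ and the figure moves with them.

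This needs no extra patients. The cost is wording and, under option (a), a less favourable power figure.

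### An exact alpha of 0.033 does not meet two-sided 5%, Sections 3.1 and 8.1 set different levels for the primary interval, and the exact test at one-sided 0.025 has 70.8% power, not 80.8%

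*Combined protocol and SAP*

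**What the plan says.** The primary analysis compares the responder proportion with a performance goal of 50% (Section 3.1.3). Its level and method appear in several places.

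- **Section 3.1:** "This will be tested with one sided 97.5% confidence interval". The same section gives the aim as "The aim of the study is to show that at least 50% of participants met the primary endpoint above" and adds "Surgical success is defined if at least 50% of participants experience at least 50% reduction in AHI and 25% reduction in ODI".
- **Section 3.2:** the assumptions are "PG=50% with 5% significance level and 80% power", with no sidedness given for the 5%. The PASS output below them is for a one-sided z-test using the null standard error, target alpha 0.025, rejecting at Z of 1.96 or more. For n=43 and a true rate of 70% it reports power 0.8081 and actual alpha 0.0330. The note reads: "Note that the one the actual exact Alpha of 0.033 will meet the two sided 5% significance".
- **Section 8.1:** the responder proportion "will be evaluated using a one-sided 95% confidence interval". Then: "Proportion with 95% CI will be given using normal approximation to the Binomial". And: "P-Value will be derived based on the exact binomial distribution of the null hypothesis". No alpha is given for that p-value.
- **Section 8.3:** repeats 80.8% as the expected power, citing Section 3.2.

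**The concern.** The PASS table tests for a proportion above 50%, so its actual alpha of 0.0330 is a one-sided error. It exceeds the one-sided target of 0.025, and it cannot be set against a two-sided 5% without doubling.

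The power in Section 8.3 was computed for a z cut-off, whereas Section 8.1 takes the p-value from the exact binomial. With 43 patients the two methods can differ by one responder, which moves the power noticeably. The interval level also differs between Sections 3.1 and 8.1, and nothing says which sentence governs.

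This is the only primary test in a single-arm study whose results go to regulatory authorities (Section 2.3). If the threshold is not fixed in advance, the same responder count can be called a success or a failure afterwards.

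**Working it through.** **Inputs.** Null rate p0 = 0.50 (Section 3.1.3). Alternative p1 = 0.70, which is 20 points above the goal (Sections 3.2 and 8.1). 43 analysed and 48 enrolled (Section 3.2). X is the number of responders, binomial, with a single final look.

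**1. Reproducing the PASS row.** The z statistic is (r/43 − 0.5)/√(0.25/43). It is 1.677 at r = 27 and 1.982 at r = 28, so Z ≥ 1.96 first holds at 28/43.
- P(X ≥ 28 | 0.5) = 0.0330
- P(X ≥ 28 | 0.7) = 0.8081

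Both match the table. The 80.8% is therefore correct for that z-test.

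**2. The note.** The null distribution is symmetric at 0.5, so the two-sided error is exactly 2 × 0.0330 = 0.0660. That is above 0.05, and 0.0330 is above 0.025.

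**3. The exact test at one-sided 0.025.** P(X ≥ 28 | 0.5) = 0.0330 does not reject; P(X ≥ 29 | 0.5) = 0.0158 does. The cut-off is 29/43 and the power is P(X ≥ 29 | 0.7) = 0.7081. Two-sided 0.05 gives the same cut-off, since 2 × 0.0158 = 0.0315 to rounding.

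**4. The candidate rules side by side (n = 43).**

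| Rule | Responders needed | One-sided error | Power at 70% |
|---|---|---|---|
| Point estimate of at least 50% (3.1, read literally) | 22 | 50.0% | 99.7% |
| Normal-approximation one-sided 95% lower bound above 50% | 27 | 6.3% | 88.3% |
| Z ≥ 1.96; normal-approximation one-sided 97.5% bound; exact test at one-sided 0.05 | 28 | 3.3% | 80.8% |
| Exact test at one-sided 0.025 or two-sided 0.05 | 29 | 1.6% | 70.8% |

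**5. Interval against p-value on the same data.** The normal-approximation lower bound is p̂ − z√(p̂(1 − p̂)/43).
- 28/43: p̂ = 0.651; the 97.5% bound is 0.509 (pass), but exact p = 0.033 fails at 0.025. The Clopper-Pearson 97.5% bound is 0.491, which agrees with the exact p.
- 27/43: p̂ = 0.628; the 95% bound is 0.507 (pass), but exact p = 0.063 fails even at 0.05. The Clopper-Pearson 95% bound is 0.491.
- 29/43: the Clopper-Pearson 97.5% bound is 0.515, so it passes together with exact p = 0.016.

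At a true rate of 70%, P(X = 28) = 0.100 and P(X = 27 or 28) = 0.175.

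**6. Does enrolling 48 restore 80%?** Exact test at one-sided 0.025, true rate 70%:

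| Analysed | 43 | 44 | 45 | 46 | 47 | 48 | 49 | 50 | 51 | 52 | 53 | 54 |
|---|---|---|---|---|---|---|---|---|---|---|---|---|
| Cut-off | 29 | 29 | 30 | 31 | 31 | 32 | 32 | 33 | 33 | 34 | 35 | 35 |
| Power (%) | 70.8 | 77.8 | 74.6 | 71.3 | 78.0 | 74.9 | 81.0 | 78.2 | 83.6 | 81.1 | 78.4 | 83.7 |

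No number from 43 to 48 reaches 80%. The 74.9% at 48 assumes no dropouts. If the 10% who drop out stay in the 48 as non-responders, and 70% is the rate among completers, the overall rate is 0.9 × 0.70 = 0.63 and P(X ≥ 32 | 48, 0.63) = 0.358. With exactly 43 completers, P(X ≥ 32 | 43, 0.70) = 0.327.

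**The case against.** The strongest reply is that 80.8% is not a miscalculation. It is right for the z-test in Section 3.2, and the table prints the actual alpha openly. Sections 3.1 and 8.1 both name an interval as the primary assessment, and Section 8.1 adds the one-sample test as a supplement. A 97.5% bound by the normal approximation passes from 28/43 and has 80.8% power, as does the exact test at one-sided 0.05, which is one reading of the 5% in Section 3.2. On this view 70.8% joins the level of Section 3.1 to the method of Section 8.1, a pairing that no single sentence makes.

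This stands in part: 70.8% is conditional on exact testing at one-sided 0.025. But the z cut-off and the normal-approximation bound keep 80.8% by allowing an actual error of 3.3% against a 2.5% target, and one-sided 0.05 contradicts Section 3.1 and the PASS target alpha. The note is false on every reading.

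Other fair points:
- The sentences about at least 50% of participants are probably loose drafting. One carries a performance-goal label, the other is followed at once by the interval test, and Section 3.1.3 states formal hypotheses. They need rewording, but the 22/43 rule is only their literal reading.
- The second interval in Section 8.1, if two-sided, has the lower limit that Section 3.1 calls for, and an approximate interval beside an exact p-value is common. The two can still disagree at 28/43.
- The dropout figures come from a separate conflict over the analysis set and do not carry this point.

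**Conclusion.** The concern holds. The note in Section 3.2 is wrong (0.066 two-sided), and Sections 3.1 and 8.1 contradict each other on the level. The stated power does not belong to the exact test at the level in Section 3.1 and the PASS output: it is 70.8% with 43 analysed, a shortfall of 80.8 − 70.8 = 10.0 percentage points, and at most 78.0% for any number from 43 to 48. The tests and bounds put the threshold at 27, 28 or 29 responders, with one-sided errors of 6.3%, 3.3% and 1.6%.

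These figures assume a true rate of 70%, independent patients and one final look. The 70.8% further assumes that the exact p-value is judged at one-sided 0.025 or two-sided 0.05. Among the levels the plan names, the exact test has 80.8% power only at one-sided 0.05. This must be fixed before any outcome data are examined.

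**What to change.** State one success rule, identically, in Sections 3.1, 3.2 and 8.1: exact one-sided binomial p of at most 0.025, equivalently a one-sided 97.5% Clopper-Pearson lower bound above 50%, with the critical count set by the number analysed (29 for 43). Then:

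- **Section 3.1:** reword both sentences about at least 50% of participants so that they state the performance goal, not a separate criterion.
- **Section 3.2:** delete the 0.033 note, and replace the 5% and 80% assumptions with one-sided 0.025 and the achieved power.
- **Section 8.1:** change the one-sided 95% interval to one-sided 97.5%, and report the two-sided 95% Clopper-Pearson interval in place of the normal-approximation one.
- **Sections 3.2 and 8.3:** give power as 70.8% for 43 analysed at a true rate of 70%. If 74.9% is quoted for 48, label it as assuming no dropouts, and first settle whether dropouts are excluded (3.1.2, 8.4) or counted as failures (3.1.1, 8.5).

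**Alternative.** If the sponsor intends one-sided 0.05 with the exact test, 28/43 and 80.8% stand. Section 3.1 and the PASS target alpha must then change, the weaker standard must be declared, and the note must still go.

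**Cost.** Either route changes wording only and adds no patients. The 0.025 route admits that the 80% target is missed. Reaching it takes 49 analysed (81.0%), one more than the planned enrolment before any dropout; power dips below 80% again at 50 and 53 and stays above it from 54.

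Both rules are for a single final look. The interim analyses in Section 8.6 have no alpha rule and need separate treatment.

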3.3 Secondary Efficacy Endpoints

To determine whether multi-level radiofrequency ablation of the upper airway in adults with OSAS with the CelonProSleep *plus* bipolar electrode improves daytime sleepiness, snoring, percentage sleep

time at $\text{SaO}_2 < 90\%$, and sleep-related quality of life without a significant increase in pain, speech or swallowing dysfunction.

The following tools will be applied in order to determine the secondary aims: (1) Epworth Sleepiness Scale (ESS); (2) Functional Outcomes of Sleep Questionnaire (FOSQ), (3) SaO_2 , and (4) 100 mm VAS scale concerning snoring. ESS, FOSQ, and $\text{VAS}_{\text{snoring}}$ will be assessed at Baseline, 6 weeks after completion of each upper airway RF ablation treatments, and 6 months post-treatment. The percentage sleep time with $\text{SaO}_2 < 90\%$ will be determined at the final 6-month PSG.

Secondary endpoint statistical analysis includes descriptive statistics of percentages, Means and SD; In cases in which inference will be added to the value, it will be then corrected with Holm's adjustment for testing multiplicity.

